14.2 Demographic and Baseline Characteristics

The following demographic variables at screening will be summarized by dose level: race, gender, age, height and weight.

14.3 Analysis of Primary Endpoint

Primary outcome: Number of migraine/migrainous days in the 5th-8th weeks of randomized treatment between melatonin (combined 6 mg+3mg) vs. placebo. We will control for baseline migraine/migrainous day frequency in the 5-8th week of the single-blind treatment phase and use an ANCOVA analysis.

Definition of migraine/migrainous day:

- 1) Patient had a moderate or severe headache and took a migraine-specific medication (triptan or ergot)
- 2) Patient had a moderate or severe headache; headache lasted for at least 2 hours, and
 - a. At least one of the following was present (throbbing quality, movement sensitivity, or unilateral/bilateral location) AND
 - b. At least one of the following was also present (photophobia, phonophobia, nausea or vomiting)

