Uncontrolled work in pediatrics also suggests melatonin may be useful in the treatment of pediatric and adolescent migraine. In one study, 60 pediatric and adolescent participants were treated with up to 6 mg melatonin nightly (formulation unspecified). At three months, mean(SD) migraine attack frequency decreased from 15.6 ± 7.6 to 7.1 ± 4.4 per month¹⁰. In a smaller open-label pediatric study, 14 migraineurs were treated with 3 mg melatonin nightly. Ten (71%) had a $\geq 50\%$ improvement in headache frequency at 3 months¹¹. Melatonin was well tolerated in these pediatric studies: in the study where children received up to 6 mg of melatonin, 7(12%) had daytime sleepiness vs. 1(7%) in the smaller study where they received 3 mg^{10,11}.

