8 STUDY TREATMENTS

8.1 Method of Assigning Subjects to Treatment Groups

Randomization: 1:1:1 to melatonin 3 mg: 6 mg: placebo. Randomization will be done in blocks of 6 by site. A computer-generated scheme will be used to generate the randomization.

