14.6 Sample Size and Randomization

To detect a difference of 1.1 migraine/migrainous days (SD 1.8) between groups, as was seen in the adolescent topiramate migraine prevention trial that led to FDA-approval of that agent in 12-17 year-olds, we need outcome data on 42 participants/arm. We anticipate that 25% of enrolled participants will be screened out by the single-blind placebo run-in process, and that 85% of those who randomize will complete the trial. Therefore we will enroll 70 per arm, or $n=210$ total.

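### The primary ANCOVA names no standard-error type for a 2:1 contrast of day counts; the default error is slightly wrong, in either direction, if treatment changes the spread

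*Combined protocol and SAP*

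**What the plan says.** Section 14.3 defines the primary outcome as "Number of migraine/migrainous days in the 5th-8th weeks of randomized treatment between melatonin (combined 6 mg+3mg) vs. placebo". The method is one sentence: "We will control for baseline migraine/migrainous day frequency in the 5-8th week of the single-blind treatment phase and use an ANCOVA analysis". The synopsis and section 3.1 repeat it. Section 14.1 names STATA as the software. Nowhere do the documents state a standard-error type, a variance assumption or a count model for this analysis.

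Section 8.1 gives "Randomization: 1:1:1 to melatonin 3 mg: 6 mg: placebo", so the pooled contrast has two melatonin patients for each placebo patient.

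The only SD given for planning is a common one, in section 14.6: "To detect a difference of 1.1 migraine/migrainous days (SD 1.8) between groups", from which "we need outcome data on 42 participants/arm". No arm means or arm-specific SDs appear.

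**The concern.** The default ANCOVA standard error pools the residual variance over both groups. With equal group sizes this does little harm when the variances differ. At 2:1 the pooled variance is dominated by the larger group, while the true uncertainty depends most on the smaller one. If the variances differ, the standard error is biased, and so are the confidence interval and any test away from the null.

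Unequal variances are plausible here. The outcome is a bounded count, and the spread of such counts often rises with the mean. Section 1 reports an open-label paediatric study in which "mean(SD) migraine attack frequency decreased from" 15.6 (SD 7.6) to 7.1 (SD 4.4) per month. If melatonin shifts the mean, it may also change the spread.

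At stake is the accuracy of the interval around the primary estimate when there is an effect to estimate. The test of no effect is not at stake: if melatonin leaves the distribution of days unchanged, the variances are equal.

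**Working it through.** **1. Reproduce the plan's figure.** The inputs from 14.6 are a difference of 1.1 days and an SD of 1.8. Alpha and power are not stated; two-sided 5% and 80% are inferred because they return the plan's number:

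n per arm = 2 × (1.960 + 0.842)² × 1.8² / 1.1² = 2 × 7.849 × 3.24 / 1.21 = 42.03.

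This matches 42. The primary contrast is then 42 placebo against 84 melatonin. The stated losses ("25% of enrolled participants will be screened out by the single-blind placebo run-in process" and "85% of those who randomize will complete the trial") leave 70 × 0.75 × 0.85 = 44.6 per arm. Using 45 against 90 does not change the results below to the precision shown.

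**2. Bias of the pooled standard error.** Set the placebo residual variance to 1 and the melatonin residual variance to r. The documents do not give r, so it is an assumption.

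- Pooled variance: (41 + 83r) / 124
- Model SE²: pooled variance × (1/42 + 1/84)
- True SE²: 1/42 + r/84
- Approximate coverage: 2Φ(1.979 × SE ratio) − 1, where SE ratio = model SE / true SE

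Example, r = 0.8: the pooled variance is 107.4/124 = 0.866. Model SE² = 0.866 × 0.03571 = 0.03093 and true SE² = 0.02381 + 0.00952 = 0.03333. The SE ratio is √0.928 = 0.963.

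| r | SE ratio | Coverage |
|---|---|---|
| 0.5 | 0.894 | 92.3% |
| 0.7 | 0.942 | 93.8% |
| 0.8 | 0.963 | 94.3% |
| 1.0 | 1.000 | 95.2% |
| 1.25 | 1.038 | 96.0% |

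The reference value is 95.2% because the approximation combines a t critical value with a normal probability. At 42 against 42 the SE ratio is 1.000 for any r, so pairwise comparisons of two equal arms are unaffected.

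**3. Tie r to the design effect.** Let melatonin lower an assumed placebo mean m by 1.1 days. If variance follows the mean, r = (m − 1.1)/m. If it follows the squared mean, r is the square of that.

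| m (assumed) | r, mean | SE ratio | Coverage | r, squared mean | SE ratio | Coverage |
|---|---|---|---|---|---|---|
| 4 | 0.725 | 0.948 | 93.9% | 0.526 | 0.900 | 92.5% |
| 6 | 0.817 | 0.967 | 94.4% | 0.667 | 0.935 | 93.6% |
| 8 | 0.863 | 0.975 | 94.7% | 0.744 | 0.952 | 94.0% |
| 10 | 0.890 | 0.981 | 94.8% | 0.792 | 0.962 | 94.3% |

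**4. Simulated ANCOVA.** The outcome was an overdispersed count bounded at 28 days, with baseline at least 4 days. Each scenario had 8,000 simulated trials (Monte Carlo error about 0.24 percentage points) and assumed placebo means of about 7.5, 9.3 and 11.1 days.

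| Scenario | Residual variance ratio | Model SE / empirical SD | Coverage, model-based | Coverage, HC3 |
|---|---|---|---|---|
| No effect | 1.01 to 1.02 | 1.000 to 1.006 | 94.8% to 95.3% | 95.0% to 95.3% |
| Every patient reduced 15% (1.1 to 1.65 days) | 0.89 to 0.92 | 0.970 to 0.978 | 94.3% to 94.6% | 95.1% to 95.3% |
| Same mean reduction, only a subset responding | 1.12 to 1.35 | 1.03 to 1.04 | 95.8% to 95.9% | 95.2% to 95.7% |

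The direction reverses between the last two rows although the mean effect is the same.

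**5. Dose differences.** If the 3 mg and 6 mg means differ by d days, an even split adds d²/4 to the residual variance of the pooled arm. This also pushes r upward, towards an interval that is too wide.

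**The case against.** The strongest objection is that the plan contains no error to correct. It does not say that model-based errors will be used, and section 14 does not mention a confidence interval. That stands: the default is inferred from silence, so the point is about specification.

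A reader might go further and infer that an effective melatonin necessarily makes the interval too narrow. The documents do not support this. The crossover trial in section 1 gives attack frequencies of 2.9 (SD 1.4) on placebo and 2.8 (SD 1.6) on melatonin, against 4.2 (SD 1.2) at baseline, so the spread rose as the mean fell. Those SDs give r = (1.6/1.4)² = 1.306 and, by step 2, an SE ratio of 1.046 and coverage of about 96%. That trial was null, in adults, and counted attacks, so it does not settle the direction. It does show that the direction is open.

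A reader might also put the open-label SDs of 7.6 and 4.4 into the formula: r = 0.335, SE ratio 0.84, coverage about 90%. These are raw before-and-after SDs from one uncontrolled cohort whose mean fell by 8.5, not between-arm ANCOVA residual SDs. They say nothing reliable about a trial designed for 1.1 days.

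Finally, the distortion is small and the test is valid if melatonin does nothing. Both are correct, and they set the severity.

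**Conclusion.** The point holds as a minor gap. The contrast is 2:1, the outcome is a bounded count, and the standard-error type is unstated. If the default is used, the primary interval will be slightly wrong whenever treatment changes the spread, and the sign cannot be known beforehand.

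At 1.1 days and assumed placebo means of 4 to 10 days, the standard error is about 2% to 5% too small if variance follows the mean, and up to 10% too small if variance follows the squared mean and the placebo mean is 4. Under partial response it is about 3% to 4% too large. These sizes rest on the assumed means and variance laws, because the documents give only a common SD. The 5% type I error is unaffected when melatonin leaves the distribution of days unchanged.

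**What to change.** In section 14.3, state that the primary ANCOVA, adjusted for baseline migraine/migrainous days, will use heteroscedasticity-robust (HC3) standard errors for the test and the 95% confidence interval of the melatonin effect. The point estimate does not change. This removes the need to guess the direction: HC3 coverage was 95.0% to 95.7% in the simulations, including proportional reductions of 10% to 30%.

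The cost is one sentence and one option in the analysis code. If the variances are equal, the interval is about 1% to 2% wider. Under those proportional reductions it was about 2% to 7% wider than the model-based interval, much of which is the correction needed. Sample size and conduct are unaffected.

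Optionally, fit one three-arm model and take both the pooled contrast (equal weight for 3 mg and 6 mg) and the dose comparisons from it. This fixes what the pooled effect estimates and supplies a method for secondary outcomes 1 to 3 in section 14.4, where none is named. It made no material difference to the primary result in simulation, so it is a preference. The choice should be recorded before unblinding.

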6.2 Inclusion Criteria

1. Age 10-17—inclusive
2. Weight ≥ 40 kg, so as not to require mg/kg based dosing
3. Meets International Classification of Headache Disorders III beta¹ criteria for migraine in children/adolescents (international standard diagnostic criteria for research)
4. Lives in the state of California- to allow shipping of study medication from our pharmacy
5. Has at least one parent who speaks English—in order to ensure good communication with study team by phone
6. Has daily access to a smartphone in order to provide daily headache diary data
7. A Parent/Guardian consents and the adolescent is cognitively capable of giving assent to participate
8. Either not on a migraine preventive medication, or if on one the dose has been stable for at least 4 weeks prior to enrollment, or are willing to wait to start the study until they have reached a stable dose for 4 weeks
9. Willing to not use OTC melatonin or change migraine preventives during the trial
10. Has ≥ 1 headache day per week, or 4-28 days of headache in a 28-day period
Episodic headaches have been present for a minimum of 6 months—This lowers the likelihood of a secondary cause of headaches

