6.3 Exclusion Criteria

1. Continuous headache
2. History of seizures/epilepsy
3. Pregnant/lactating
4. Concomitant opioid or barbiturate overuse, wherein overuse is defined as ≥ 4 days per month of barbiturate containing compounds, ≥ 10 days per month of opioid containing compounds as these may impact sleepiness scales
5. If in the investigator's opinion there is a medical or psychiatric concern that makes them think the participant should not participate
6. Inability to swallow pills after teaching and practice
History of nocturnal asthma, as evidenced by a having a diagnosis of asthma and symptoms that manifest as nighttime awakening due to cough, wheeze, and/or shortness of breath

Randomization Criteria:

1. Had 4-28 migraine/migrainous days in the 28-day period of weeks 5-8 of single-blind placebo treatment phase, but not continuous headache.

2. At least 80% compliance with headache diary (i.e. at least 23 headache diary days) during weeks 5-8 of single-blind placebo treatment phase.

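### Does counting either one-sided or two-sided pain as a migraine feature spoil the primary endpoint's day definition?

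*Combined protocol and SAP*

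**What the plan says.** Section 14.3 names the primary outcome as "Number of migraine/migrainous days in the 5th-8th weeks of randomized treatment between melatonin (combined 6 mg+3mg) vs. placebo", analyzed by ANCOVA with the count from weeks 5-8 of the placebo run-in as covariate. It gives two numbered routes by which a day can count.

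- **Route 1:** a moderate or severe headache treated with a triptan or ergot. Pain location plays no part.
- **Route 2:** this opens with "Patient had a moderate or severe headache; headache lasted for at least 2 hours, and" and then sets two conditions. Item 2a is "At least one of the following was present (throbbing quality, movement sensitivity, or unilateral/bilateral location) AND". Item 2b asks for at least one of light sensitivity, sound sensitivity, or nausea or vomiting.

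The randomization criteria under section 6.3 use the same kind of day: "Had 4-28 migraine/migrainous days in the 28-day period of weeks 5-8 of single-blind placebo treatment phase, but not continuous headache". Section 6.2 admits only participants for whom the diagnostic entry "Meets International Classification of Headache Disorders III beta" holds, in its form for children and adolescents. Section 10.1 has a pediatric headache neurologist review the history. All headache days are a separate secondary endpoint (sections 5.2 and 14.4). Section 14.6 powers the trial on an absolute difference of 1.1 days with SD 1.8.

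**The concern.** Items 2a and 2b are set out as two hurdles joined by a capitalized conjunction, so a reader expects each to exclude something. Unilateral and bilateral together cover nearly every headache, and nothing in the documents narrows the second term to a region or shows the diary's response options. Item 2a then does no work. Route 2 becomes moderate or severe pain, at least 2 hours, and one associated symptom.

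If that were harmful, the harm would reach far. The same count supplies the primary outcome, the covariate, the three dose-specific comparisons of migraine/migrainous days and entry to randomization. A day with neither throbbing nor movement sensitivity could help someone qualify and then count as outcome. If melatonin acts only on more typical migraine days, one might expect a diluted effect and lost power.

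**Working it through.** **1. The plan's own figure.** Inputs from section 14.6: difference 1.1, SD 1.8. Two-sided alpha of 5% and power of 80% are assumed, because they are not stated there. n per arm = 2 × [1.8 × (1.960 + 0.842) / 1.1]² = 42.03, which matches the stated 42. The figure does not depend on item 2a. With 1:1:1 allocation, the primary comparison is 42 against 84, and power at these values is 90%.

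**2. What item 2a excludes.** Take days that already meet the severity and duration conditions, without a triptan or ergot. Cross throbbing (yes/no), movement sensitivity (yes/no), location (unilateral/bilateral) and three associated symptoms (yes/no, with nausea or vomiting as one): 2⁶ = 64 patterns. These are unweighted patterns, not frequencies of days.

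| Rule for 2a | Pass 2a | Pass 2a and 2b |
|---|---|---|
| As written | 64 | 56 |
| Unilateral only | 56 | 49 |
| Location removed | 48 | 42 |

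The literal reading is confirmed. Only a strictly midline headache, if the diary allows one, could fail on location and so be excluded by 2a. Item 2b still removes 8 of 64, on top of the severity and duration conditions.

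**3. Effect on the tested difference.** Let T be counted days that respond, U counted days that do not, and r the proportional reduction in T.

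- Broad count: (T + U) − [T(1 − r) + U] = Tr.
- Narrow count: T − T(1 − r) = Tr.

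The absolute difference is the same. For illustration, assume 8 counted days of which 20% do not respond: U = 1.6 and T = 6.4. Neither value is in the documents. A difference of 1.1 days then means r = 1.1/6.4 = 17.2%. As a share of the broad count it is 1.1/8 = 13.75%, smaller by one fifth. Only that relative figure shrinks, and the ANCOVA does not test it. For the same reason, setting 1.6 extra days beside the 1.1-day target compares a level with a difference.

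**4. Extra variance.** Unresponsive days can add noise. If the SD were 2.0 or 2.2 instead of 1.8, with the difference still 1.1, power at 42 against 84 would be 83% or 75%. These SDs are illustrations. Part of any added spread is stable within a person and would be absorbed by the baseline covariate. The 1.8 comes from a cited topiramate trial whose day definition is not given, so it cannot be tied to a narrow or a broad count.

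**5. The opposite case.** Suppose melatonin reduces all counted days in proportion. Removing 10%, 20% or 30% of them cuts the difference to 0.99, 0.88 or 0.77. With the SD held at 1.8, power falls from 90% to 83%, 74% or 62%. If the SD also fell in proportion, at 20% it would be 1.8 × 0.8 = 1.44, and 0.88/1.44 = 1.1/1.8 = 0.611, so power would not change. In this case narrowing brings a loss or no gain.

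**6. Effect on eligibility.** The threshold is 4 days. Removing 20% of days takes a 4-day participant to 3.2, and removing 30% takes a 5-day participant to 3.5. Both would fail, and losses could exceed the 25% planned for the run-in in section 14.6.

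**The case for a change.** The strongest argument is that a written component of a primary endpoint should do something. If breadth is intended, 2a is superfluous; if selectivity is intended, 2a fails to provide it. Since all headache days are already a secondary endpoint, the primary was meant to be more specific. Removing location would cost one line and one scoring rule, using features the definition already names.

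The logical point stands: 2a is close to redundant, and a day can count with neither throbbing nor movement sensitivity. The inference from it does not stand. Such days are not shown to be non-migraine. They pass three other conditions in diagnosed participants, the endpoint's name deliberately reaches to migrainous days, and the classification that would settle the matter is cited but not reproduced. The primary count also remains narrower than all headache days.

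The remedy goes further than the argument. The difficulty lies in pairing the two locations, yet deleting location also discards the unilateral feature, which does discriminate (49 against 42 patterns in the table).

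Items 1 and 2 lack an explicit connector, but the reading is clear. Each opens with the same severity condition, which would be pointless if both had to be met, so an analyst would score them as alternatives.

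**Conclusion.** No change to the plan is needed. Item 2a adds essentially no restriction as worded, so the endpoint is somewhat less specific than its layout suggests. The definition can be scored exactly as written, and it applies identically across the blinded arms, at baseline and at randomization, so no bias toward an arm arises. If the extra days do not respond, the tested absolute difference is unchanged and the only cost is variance that the documents do not allow anyone to size. The illustrative SDs of 2.0 and 2.2 correspond to 83% and 75% power against 90%. If the extra days do respond, a narrower count gains nothing and may lose power. The documents do not say which holds, and the melatonin studies described in section 1 report largely on headache frequency, which gives no ground for assuming that these days are unaffected.

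Redefining the day would therefore trade one reasonable endpoint for another and would also alter who can be randomized. Stating how the diary records location, writing the connector between the two routes, or adding a sensitivity count that requires throbbing, movement sensitivity or unilateral pain would be harmless tidying. The trial's conclusion does not depend on any of them.

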14.4 Analysis of Secondary Endpoints

Secondary outcome measures will include $\geq 50\%$ responder rates, tolerability (as measured by CASQ scores), and need for use of acute headache medications. Safety and tolerability data will be summarized by treatment group. Adverse event rates will be coded by body system. Adverse events will be tabulated by treatment group and will include the number of patients for whom the event occurred, the rate of occurrence, and the severity and relationship to study drug.

Secondary outcomes:

(We will control for the baseline level of these outcomes in all of these analyses)

Effectiveness secondary outcomes:

1. Number of migraine/migrainous days in the 5th-8th weeks of randomized treatment between **melatonin 3 mg vs. placebo**.

2. Number of migraine/migrainous days in the 5th-8th weeks of randomized treatment between **melatonin 6 mg vs. placebo**.
3. Number of migraine/migrainous days in the 5th-8th weeks of randomized treatment between **melatonin 3 mg vs. 6 mg**.
4. Mean headache days in 5th-8th randomized phase in melatonin (combined) vs. placebo, (followed by melatonin 3 mg vs. placebo, melatonin 6 mg vs. placebo, and melatonin 3 mg vs. melatonin 6 mg using t-tests).
5. Mean acute medication use days in 5th-8th randomized phase in melatonin (combined) vs. placebo, (followed by melatonin 3 mg vs. placebo, melatonin 6 mg vs. placebo, and melatonin 3 mg vs. melatonin 6 mg using t-tests).
6. Mean PedMIDAS score (continuous) in 5th-8th randomized phase in melatonin (combined) vs. placebo, (followed by melatonin 3 mg vs. placebo, melatonin 6 mg vs. placebo, and melatonin 3 mg vs. melatonin 6 mg using t-tests).
7. $\geq 50\%$ responder rate in 5th-8th randomized phase in melatonin (combined) vs. placebo (Chi-square or Fisher's exact (if needed), (followed by melatonin 3 mg vs. placebo, melatonin 6 mg vs. placebo, and melatonin 3 mg vs. melatonin 6 mg using Chi-square (or Fisher's exact)).

Safety outcomes:

1. Proportion with adverse events between groups
 - a. Proportion with serious adverse events between groups
 - b. Proportion of adverse events thought to be related to the study treatment
2. Mean Sleepiness score in 5th-8th randomized phase in melatonin (combined) vs. placebo, (followed by melatonin 3 mg vs. placebo, melatonin 6 mg vs. placebo, and melatonin 3 mg vs. melatonin 6 mg using t-tests).

Trial design assessment outcome:

1. Proportion of participants on melatonin who correctly guessed they were on it (just playing chance, 66% should guess melatonin)
2. Proportion of participants on melatonin who guessed their dose correctly (by chance 50% 3 mg, 50% 6 mg).
3. Proportion of participants on placebo who correctly guessed they were on placebo (by chance, 33% should guess this)
4. The same three above but with investigators guessing.

